6.3 Missing Data Imputation

Missing Data Imputation for SVR

HCV RNA values will be selected for analysis based on the analysis windows defined in Section 6.2.

For analyses of SVR, subjects missing visit values will have backward imputation applied, if possible. For backward imputation, if the nearest HCV RNA value after the SVR window is unquantifiable or undetectable, then it will be used to impute the HCV RNA value in the SVR window. If a subject is missing an HCV RNA value within the appropriate SVR window after performing backward imputation, then this value will be imputed with an HCV RNA value from a local laboratory if present; otherwise, the HCV RNA value will be missing. Subjects with missing HCV RNA data in the analysis window, after imputations, will be imputed as a failure.

Regardless of the imputation method described above, if a subject starts another treatment for HCV, then all HCV RNA values for this subject measured on or after the start date of the new HCV treatment will be excluded from analyses. The subject will be considered a failure for summaries of viral response at all time points after the start of the new HCV treatment.

Missing Data Imputation for Virologic Failure

If HCV RNA values from the central laboratory are missing but a local laboratory value is present in the appropriate time period, then the local laboratory value will be used to assess post-treatment relapse and on-treatment virologic failure.

Missing Data Imputation for PRO Questionnaires

The handling of missing data for patient reported outcomes (PROs) will be as follows. If a respondent answers at least 50% of the items in a multi-item scale of the SF-36v2, the missing items will be imputed with the average score of the answered items in the same scale. In cases where the respondent did not answer at least 50% of the items, the score for that domain will be considered missing. The Mental and Physical Component Summary measures will not be computed if any domain is missing. The missing items of the FSS questionnaire will be imputed with the average score of the answered items as long as more than 50% of the items on the FSS are answered. For EQ-5D-3L index and VAS scores, no imputation will be performed for missing items.

7.0 Demographics, Baseline Characteristics, Medical History, and Other Medications

Demographics and baseline characteristics will be summarized on the safety population overall and by type of transplant (liver or kidney).

The safety population will be used to summarize medical history and previous, concomitant, and post-treatment medications.

7.1 Demographic and Baseline Characteristics

Categorical demographic and baseline characteristic variables will be summarized with the number and percentage of subjects. Continuous variables will be summarized with descriptive statistics (number of non-missing observations, mean, standard deviation, median, maximum and minimum).

Continuous demographic variables include age, weight, height, and body mass index (BMI). Categorical demographic variables include sex, race, black race (black or nonblack), ethnicity, age category (< 65 or \geq 65 years; < 75 or \geq 75 years), BMI category (< 30, or \geq 30 kg/m²), country, and geographic region (North America, Europe, or rest of world [ROW]).

When defining geographic region, sites in the United States, Canada, and Puerto Rico will be grouped under North America; sites in Italy, Spain, and the United Kingdom will be grouped under Europe; sites in Australia, New Zealand, and Taiwan will be grouped together as ROW).

Continuous baseline characteristics include baseline log₁₀ HCV RNA level, homeostasis model of assessment – insulin resistance (HOMA-IR), creatinine clearance, eGFR, platelet count, albumin, GGT, LDL, HDL, APRI, FIB-4, AST, ALT, total, direct, indirect bilirubin, and time since transplantation (months).

Categorical baseline characteristics include:

- HCV genotype (1, 2, 3, 4, 5, or 6) and available subtype (as determined by the central laboratory);
- Prior HCV treatment history (treatment-naïve or treatment-experienced);
 - For treatment-experienced subjects, type of previous regimen (IFN-, SOF-based, or other);
 - For treatment experienced subjects, type of non-response to previous treatment (on-treatment non-responder or breakthrough, post-treatment relapse, or unknown/other);

- For treatment-experienced subjects, occurrence of prior HCV treatment relative to renal or liver transplant (pre-transplant or post-transplant);
- Prior HCV DAA treatment history:
 - DAA-naïve (i.e., treatment naïve or treatment-experienced with IFN or pegIFN with or without RBV);
 - SOF-experienced (i.e., treatment-experienced with sofosbuvir with RBV with or without pegIFN);
 - Other DAA-experienced (i.e., treatment-experienced with DAA drugs other than sofosbuvir);
- IL28B genotype (CC, CT, or TT; CC or non-CC);
- Baseline HCV RNA level (< 1,000,000 or ≥ 1,000,000 IU/mL; < 6,000,000 or ≥ 6,000,000 IU/mL);
- Baseline creatinine clearance ($< 60, \ge 60$ to $< 90, \ge 90$ mL/min);
- Baseline eGFR (< $60, \ge 60$ to < $90, \ge 90$ mL/min/1.73 m²);
- Baseline fibrosis stage (equivalent to Metavir F0 F1, F2, F3, or F4 [if applicable]);
- Baseline platelet count (< 90 or \ge 90 × 10⁹/L);
- Baseline albumin (< 35 or \geq 35 g/L);
- History of diabetes (yes/no);
- History of bleeding disorders (yes/no);
- History of depression or bipolar disorder (yes/no);
- History of cardiovascular disease (yes/no);
- Type of transplant (liver or kidney),
 - For renal transplant subjects, prior dialysis type (hemodialysis, peritoneal dialysis, other, or not done);
- Donor type (living or deceased);
- Immunosuppressant medication (Tacrolimus, Cyclosporine, other);
- Injection drug user (yes, within last 12 months; yes, more than 12 months ago; or no);
- Subject on stable opiate substitution (yes/no);

- Tobacco use (user, ex-user, or non-user);
- Alcohol use (drinker, ex-drinker, or non-drinker);
- Concomitant use of Proton Pump Inhibitors (PPIs).

Summaries of baseline resistance are described in Section 10.8.

Any concomitant medication coded to the WHO Drug Dictionary ATC code of A02BC will be counted as a PPI.

If the IL28B genotype result is not available from a sample collected on Day 1, then a result available from a sample collected at any time during the study will be used to summarize IL28B genotype. IL28B rs12979860 will be resulted as C/C, C/T, or T/T by the central laboratory.

HOMA-IR is defined as fasting glucose (mmol/L) \times fasting insulin (μ IU/mL) \div 22.5. Subjects who do not have concurrent fasting glucose and fasting insulin values at baseline will be excluded from the summary of baseline HOMA-IR.

Baseline fibrosis stage is defined for subjects with non-missing liver biopsy scores, FibroScan scores, or FibroTest scores. Only one score will be used to categorize each subject even if a subject has more than one score recorded. If a biopsy score is present, then it will be used to categorize the subject, regardless of the FibroScan/FibroTest score. Similarly, if a FibroScan score is present along with a FibroTest score, then the FibroScan score will be used to categorize the subject. If biopsy and FibroScan scores are not present and more than one FibroTest result is available, then the baseline FibroTest result (i.e., last non-missing FibroTest result on or before Day 1) will be used to categorize the subject. Subjects will be categorized as F0 - F1, F2, F3, or F4 according to Table 4.

All subjects will be categorized as not having cirrhosis (cirrhosis = no) since this study excludes subjects with cirrhosis.

Baseline Fibrosis Stage, Metavir Equivalents	Liver Biopsy Metavir, Batts Ludwig, Knodell, IASL, Scheuer, or Laennec Score	Liver Biopsy Ishak Score	FibroScan (kPa)	FibroTest*
F0 – F1	0 or 1	0, 1, or 2	< 8.8	≤ 0.48
F2	2	3	\geq 8.8 to < 9.6	0.49 to 0.58
F3	3	4	\geq 9.6 to < 12.5	0.59 to 0.74
F4	4	\geq 5	≥ 12.5	≥ 0.75

Table 4.Baseline Fibrosis Stage

* APRI will not be used to derive Baseline Fibrosis Stage. However, per inclusion/exclusion criteria, subjects need to have concordant FibroTest and APRI scores in order to determine eligibility.

Immunosuppressant medications (i.e., Cyclosporine, Sirolimus, Everolimus and Tacrolimus) are captured on the "Immunosuppression Regimen Dosing Diary" eCRF. Other immunosuppressant medications are captured on the "Concomitant Medications and Supplements" eCRF.

Baseline APRI and FIB-4 are defined as the equations below. Subjects who do not have concurrent AST and platelet values at baseline will be excluded from the summary of baseline APRI. Age is defined in years at baseline. Subjects who do not have concurrent baseline values of AST, ALT, and platelet count or subjects who are missing age will be excluded from the summary of FIB-4.

$$APRI = \frac{\frac{AST \text{ Level (U/L)}}{AST (Upper \text{ Limit of Normal)(U/L)}} \times 100$$

$$Platelet \text{ Count (109/L)} \times AST \text{ Level (U/L)}$$

$$FIB-4 = \frac{Age (years) \times AST \text{ Level (U/L)}}{\sqrt{100}}$$

$$B-4 = \frac{1}{\text{Platelet Count (10^{9}/\text{L})} \times \sqrt{\text{ALT (U/L)}}}$$

Histories of diabetes, bleeding disorders, depression or bipolar disorder, and cardiovascular disease will be based on the Medical History (MH) eCRF, as defined in Table 5.

Table 5.Medical History eCRF

	Medica	l History eCRF
Subgroup	Body System	Condition/Diagnosis
Diabetes	Metabolic	Diabetes mellitus
Bleeding disorders	Blood	Clotting/bleeding problems Factor deficiency Hemophilia Von Willebrand disease
Depression or bipolar disorder	Neurologic and Psychiatric System	Bipolar disorder Depression
Cardiovascular disease	Cardiovascular	Angina Cardiac arrhythmia Cardiovascular disease Congenital heart disease Congestive heart failure Coronary artery disease Hypertension Myocardial infarction Myocarditis Peripheral vascular disease-arterial Peripheral vascular disease-venous Valvular heart disease Vasculitis

7.2 Medical History

Medical history data will be summarized and presented using body systems and conditions/diagnoses as captured on the eCRF. The body systems will be presented in alphabetical order and the conditions/diagnoses will be presented in alphabetical order within each body system. The number and percentage of subjects with a particular condition/diagnosis will be summarized. Subjects reporting more than one condition/diagnosis within a body system will be counted only once for that body system.

7.3 Prior, Concomitant and Post-Treatment Medications

A prior medication is defined as any medication taken prior to the date of the first dose of study drug (ABT-493/ABT-530). A concomitant medication is defined as any medication that started prior to the date of the first dose of study drug and continued to be taken on or after the first dose of study drug or any medication that started on or after the date of the first dose of study drug, but not after the date of the last dose of study drug. A post-treatment medication for the treatment of HCV is defined as any medication taken on or after the last dose of study drug and entered as "Post-treatment HCV medications" on the eCRF.

The number and percentage of subjects taking prior medications, concomitant medications, and post-treatment HCV medications will be summarized by generic drug name based on the WHO Drug Dictionary. The prior HCV medications taken by the treatment experienced subjects will be summarized separately from other prior medications.

The number and percentage of subjects taking concomitant immunosuppressant medications will be summarized separately from other concomitant medications.

The number and percentage of subjects with immunosuppressant medication dosage increase and decrease, respectively, at each post-baseline visit in the treatment period will be summarized by each immunosuppressant medication as captured on the "Immunosuppression Regimen Dosing Diary" eCRF (i.e., Cyclosporine, Sirolimus, Everolimus and Tacrolimus).

8.0 Patient Disposition

The number and percentage of subjects who screen failed for any reason, and for each screen fail reason, will be summarized for all subjects who screen failed.

8.1 Disposition of Safety Population

The number of subjects in each of the following categories will be summarized overall and by investigator.

- Subjects enrolled in this study;
- Subjects who took at least one dose of study drug;
- Subjects who completed study drug;
- Subjects who prematurely discontinued study drug;
- Subjects who completed the study;
- Subjects who prematurely discontinued from the study;
- Subjects ongoing in the Post-Treatment Period at the time of the primary analysis.

The number and percentage of subjects who discontinued study drug will be summarized by reason (all reasons) and by primary reason (per eCRF). Similar summaries will be provided for discontinuations from the study.

The number and percentage of subjects with reported study drug interruptions will be summarized.

Reasons for study drug interruptions will be presented in the CSR listings.

9.0 Study Drug Exposure and Compliance

9.1 Exposure

The duration of exposure to study drug will be summarized for the safety population. Duration of exposure is defined for each subject as the last study drug dose date minus the first study drug dose date plus 1 day.

Descriptive statistics (mean, standard deviation, median, minimum, and maximum) will be presented for exposure during the treatment period.

ABT-493/ABT-530

ABT-493/ABT-530 M13-596 – Statistical Analysis Plan Version 1.0 – 27 October 2016

Study drug duration will be summarized with frequencies and percentages using the following categories:

- 1 to 15 days
- 16 to 30 days
- 31 to 45 days
- 46 to 60 days
- 61 to 75 days
- 76 to 90 days
- > 90 days

In addition, the number and percentage of subjects with study drug duration of \geq 77 days will be summarized.

9.2 Compliance

At each visit (starting with the Week 4 visit) during the Treatment Period, the total number of tablets dispensed and returned is recorded. The compliance for study drug (ABT-493/ABT-530) during the treatment period will be calculated as the percentage of tablets taken relative to the total tablets expected to be taken. The total number of tablets expected to be taken will be equal to the total number of tablets that should have been taken per the protocol for the duration that the subject was in the Treatment Period (date of last dose of study drug – date of first dose of study drug + 1). Study drug interruptions recorded on the eCRF will not be subtracted from the duration.

A subject is considered to be compliant if the percentage is between 80% and 120%. Compliance will be calculated for each subject and summarized with the mean, median, standard deviation, minimum, and maximum. The percentage of compliant subjects will be summarized for study drug, based on data as observed. An additional summary of the percentage of compliant subjects will be provided where subjects who are missing study drug accountability records will be imputed as non-compliant.

10.0 Efficacy Analysis

10.1 General Considerations

General Considerations

All efficacy analyses will be performed on the ITT population, unless otherwise specified.

Missing data will be imputed as described in Section 6.3 for analyses of the HCV RNA endpoints of SVR.

Plasma HCV RNA levels will be determined for each sample collected by the central laboratory using the Roche COBAS[®] AmpliPrep/COBAS[®] TaqMan[®] HCV Quantitative Test, v2.0. The lower limit of detection (LLOD) and lower limit of quantification (LLOQ) for this assay (regardless of genotype) are both 15 IU/mL.

HCV RNA results that are detectable but not quantifiable are reported as "< 15 IU/ML HCV RNA DETECTED" and those that are undetectable are reported as "HCV RNA NOT DETECTED" in the database.

The notation "HCV RNA < LLOQ" is used to represent all HCV RNA values < 15 IU/mL, including values reported as "HCV RNA NOT DETECTED" or "< 15 IU/ML HCV RNA DETECTED." HCV RNA ≥ LLOQ are all quantifiable values of 15 IU/mL or greater.

Definitions for Efficacy Endpoints

A confirmed quantifiable value during treatment is defined as any two consecutive HCV RNA measurements \geq LLOQ (or 100 IU/mL for **Breakthrough**), either both during treatment or at the final treatment measurement and the next consecutive post-treatment measurement. A confirmed quantifiable post-treatment value is defined as any two consecutive post-treatment HCV RNA measurements \geq LLOQ.

Breakthrough = confirmed HCV RNA \geq 100 IU/mL after HCV RNA < LLOQ during the Treatment Period; or confirmed increase from nadir in HCV RNA (two consecutive

HCV RNA measurements > 1 \log_{10} IU/mL above nadir) at any time point during the Treatment Period. A single breakthrough value (≥ 100 IU/mL or > 1 \log_{10} above nadir) followed by lost to follow-up also will be considered a breakthrough (i.e., will not require confirmation).

EOT failure = HCV RNA \geq LLOQ at end of treatment with at least 6 weeks of treatment, where the HCV RNA value must be collected on or after Study Drug Day 36 and study drug duration \geq 36 days.

On-treatment virologic failure = Breakthrough or **EOT failure**.

 $SVR_4 = HCV RNA < LLOQ$ in the SVR_4 window (4 weeks after the last actual dose of study drug) without any confirmed quantifiable ($\geq LLOQ$) post-treatment value before or during that SVR window.

 $SVR_{12} = HCV RNA < LLOQ$ in the SVR_{12} window (12 weeks after the last actual dose of study drug) without any confirmed quantifiable ($\geq LLOQ$) post-treatment value before or during that SVR window.

 $SVR_{24} = HCV RNA < LLOQ$ in the SVR_{24} window (24 weeks after the last actual dose of study drug) without any confirmed quantifiable ($\geq LLOQ$) post-treatment value before or during that SVR window.

Relapse₁₂ = confirmed HCV RNA \geq LLOQ between end of treatment and 12 weeks after last actual dose of study drug (up to and including the SVR₁₂ assessment time point) for a subject with HCV RNA < LLOQ at Final Treatment Visit who completed treatment (defined as study drug duration \geq 77 days), excluding reinfection as described below.

Relapse₂₄ = confirmed HCV RNA \geq LLOQ within the SVR₂₄ window for a subject who achieved SVR₁₂ and has HCV RNA data available in the SVR₂₄ window, excluding reinfection.

Relapse_{overall} = confirmed HCV RNA \geq LLOQ between end of treatment and up to and including the last HCV RNA measurement collected in the PT Period for a subject with HCV RNA < LLOQ at Final Treatment Visit who completed treatment (defined as study drug duration \geq 77 days), excluding reinfection.

Virologic failure = On-treatment virologic failure or Relapse_{overall}.

Only subjects who have at least one post-treatment HCV RNA value will be included in analyses of relapse. For the analysis of relapse, completion of treatment is defined as any subject with study drug duration of 77 days or greater. If the last available post-treatment value is \geq LLOQ, then the subject will be considered a relapse (i.e., will not require confirmation).

HCV reinfection is defined as confirmed HCV RNA \geq LLOQ after the end of treatment in a subject who had HCV RNA < LLOQ at Final Treatment Visit, along with the post treatment detection of a different HCV genotype, subtype, or clade compared with baseline, as determined by phylogenetic analysis of the NS3 or NS5A, and/or NS5B gene sequences. Reinfection in the case of the same HCV subtype is defined as a clade switch, as indicated by the lack of clustering between the baseline and post-treatment sequences by phylogenetic analysis. If phylogenetic analysis is not possible due to technical difficulties, HCV reinfection may be determined with a confirmed HCV genotype or subgenotype switch by the Versant HCV Genotype Inno-LiPA Assay v2.0 or Sanger assay.

Post-treatment relapse is defined as described earlier (**Relapse**₁₂, **Relapse**₂₄, **Relapse**_{overall}), and no genotype, subtype, or clade switch compared with baseline as determined by phylogenetic analysis of the NS3 or NS5A gene sequences. If phylogenetic analysis is not possible due to technical difficulties, the subject will be defined as having a post-treatment relapse unless an HCV genotype or subgenotype switch is confirmed by the Versant HCV Genotype Inno-LiPA Assay v2.0 or Sanger assay.

Reasons for SVR₁₂ Non-Response

Subjects who do not achieve SVR₁₂ (SVR₁₂ non-responders) will be categorized as having:

- 1. On-treatment virologic failure (see **On-treatment virologic failure** definition);
- Relapse (defined according to the Relapse₁₂ definition for subjects who complete treatment);
- Prematurely discontinued study drug with no on-treatment virologic failure (defined as any SVR₁₂ non-responder who prematurely discontinued study drug [study drug duration < 77 days] and did not meet the **On-treatment virologic** failure definition);
- 4. HCV reinfection (see definition described earlier);
- 5. Missing follow-up data in the SVR₁₂ window (defined as any subject who completed study drug without data in the SVR₁₂ window after applying the imputation rules and not meeting the definitions of [1], [2], [3], or [4]);
- Other (defined as any SVR₁₂ non-responder not meeting the definitions of [1] [5]).

Reasons for SVR24 Non-Response

Subjects who do not achieve SVR₂₄ (SVR₂₄ non-responders) will be categorized as having:

- 1. On-treatment virologic failure (see **On-treatment virologic failure** definition);
- Relapse (defined according to the Relapse₁₂ definition for subjects who complete treatment);
- 3. Relapsed after achieving SVR₁₂ (see **Relapse₂₄** definition);
- 4. Prematurely discontinued study drug with no on-treatment virologic failure (defined as any SVR₂₄ non-responder who prematurely discontinued study drug

[study drug duration < 77 days] and did not meet the **On-treatment virologic** failure, Relapse₁₂, or Relapse₂₄ definitions);

- 5. HCV reinfection;
- 6. Missing follow-up data in the SVR₂₄ window (defined as any subject who completed study drug without data in the SVR₂₄ window after applying the imputation rules and not meeting the definitions of [1], [2], [3], [4], or [5]);
- Other (defined as any SVR₂₄ non-responder not meeting the definitions of [1] [6]).

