10.7 Additional Efficacy Analyses

The following additional efficacy endpoints will be summarized:

- The percentage of subjects with HCV RNA < LLOQ at each post-baseline visit in the Treatment Period (using data as observed);
- The percentage of DAA-naïve subjects with on-treatment virologic failure;
- The percentage of DAA-naïve subjects with post-treatment relapse;
- The percentage of subjects with SVR₄;
- The percentage of subjects with SVR₂₄;

- The percentage of subjects who relapsed after achieving SVR₁₂ (**Relapse₂₄**);
- The percentage of subjects with virologic failure through Post-Treatment Week 12 (i.e., the SVR₁₂ non-responders due to on-treatment virologic failure or Relapse₁₂)

In the above analyses for SVR, virologic failure, and relapse, the percentage of subjects with a two-sided 95% Wilson score interval will be summarized. Imputations for missing data will be performed as described in Section 6.3 for analysis of SVR, where a missing response will be imputed as a failure after performing the described imputation. All other endpoints will be presented using data as observed.

A summary of the subjects who completed treatment and relapsed (defined as **Relapse_{overall}**) will be prepared displaying the number of subjects relapsing overall and by SVR visit window (within the SVR₄, SVR₁₂, SVR₂₄ windows or after SVR₂₄ window), including the subject number and the SVR visit window corresponding to the first occurrence of relapse. A similar listing will be prepared for subjects who prematurely discontinued treatment and relapsed after having HCV RNA < LLOQ at their Final Treatment Visit.

The number and percentage of subjects who do not achieve SVR_{12} will be summarized by reason for non-response (as defined in Section 10.1). A listing of subject numbers and reason for non-response will be prepared. A similar summary and listing will be prepared for subjects who do not achieve SVR_{24} .

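### A completer with no SVR12-window sample and a quantifiable last value at Week 24 is a virologic failure by definition, but is classed as missing or other, and one sensitivity analysis counts that subject as cured

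*SAP*

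**What the plan says.** SAP 10.1 has three relapse definitions with different time limits.

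- Relapse12 runs "up to and including the SVR₁₂ assessment time point".
- Relapse24 applies only "for a subject who achieved SVR₁₂ and has HCV RNA data available in the SVR₂₄ window, excluding reinfection".
- Relapse-overall runs "up to and including the last HCV RNA measurement collected in the PT Period" and does not require SVR12.

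The general term is built on the third: "Virologic failure = On-treatment virologic failure or Relapse", where the dropped subscript is 'overall'. A quantifiable last available value needs no confirmation.

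The reason lists in the same section do not use Relapse-overall. The SVR12 list uses Relapse12 and then has a missing-data reason, "defined as any subject who completed study drug without data in the SVR₁₂ window after applying the imputation rules". The SVR24 list uses Relapse12 and Relapse24 and ends with a residual category.

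SAP 6.3 carries a later value back into the SVR window in one direction only: "if the nearest HCV RNA value after the SVR window is unquantifiable or undetectable, then it will be used to impute". Otherwise, "Subjects with missing HCV RNA data in the analysis window, after imputations, will be imputed as a failure".

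Three later parts of the SAP depend on these labels.

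- Section 5.1.2 removes from mITT-GT-VF the SVR12 non-responders whose reason is not virologic failure.
- Section 10.5.1, second approach, counts non-responders in the missing-data category as successes.
- Section 10.8 puts virologic failures, as defined in 10.1, into the PVF population. It names missing SVR12 data among the non-virologic reasons that lead to the non-PVF population.

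**The concern.** One subject can carry two incompatible labels. The 10.1 definition says that the virus came back and the treatment failed. The reason list says that nothing is known. No section says which label governs.

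The SVR12 rate in mITT-GT-VF is therefore not uniquely defined. This population also carries the baseline-variant subgroup in 10.6 and Analyses 2 and 3 in 10.8, where failures are expected to be few and the loss of one matters. The PVF and non-PVF resistance listings have the same conflict. The sharpest consequence is in 10.5.1: a rule meant for subjects with unknown outcome would record as cured a subject whose own last sample shows quantifiable virus.

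**Working it through.** The plan gives no figure for this situation, so the check is a trace through the definitions, followed by an illustration with assumed counts.

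**Conditions that define the case**

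1. Study drug duration of at least 77 days and HCV RNA < LLOQ at the Final Treatment Visit (SAP 10.1).
2. Any earlier post-treatment values < LLOQ. HCV RNA is scheduled at post-treatment Weeks 2, 4 and 8 (Protocol Appendix D). Two consecutive positives there would already meet Relapse12. A single positive at Week 8 followed by a positive at Week 24 could also be read as confirmed.
3. No central or local HCV RNA value on Days 57–126, the SVR12 window (SAP Table 2). A Week 8 sample drawn on Day 57 or later fills the window, so missing the Week 12 visit alone is not enough.
4. The last available value is ≥ LLOQ, falls on Days 127–210 (the SVR24 window), and is not reinfection.

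**Trace**

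- SVR12: nothing is carried back, because the later value is quantifiable. The window stays missing, so the subject is a failure.
- Relapse12: not met, because the positive lies beyond its time limit.
- Relapse24: not met, because SVR12 was not achieved.
- Relapse-overall: met, with confirmation waived for a last value. Virologic failure is therefore met.
- SVR12 reason: the relapse reason fails, so the subject falls to missing follow-up data.
- SVR24 reason: both relapse reasons fail, and the missing-data reason fails because SVR24-window data exist. The subject falls to other.

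**Neighbouring cases under the same rules**

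| Days 57–126 | Later value | SVR12 | Virologic failure | SVR12 reason | SVR24 reason |
|---|---|---|---|---|---|
| none | ≥ LLOQ, Day 168 | no | yes | missing | other |
| none | < LLOQ, Day 168 | yes | no | – | – |
| none | ≥ LLOQ, after Day 210 | no | yes | missing | missing |
| < LLOQ | ≥ LLOQ, Day 168 | yes | yes | – | relapse after SVR12 |

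The first two rows show the asymmetry: the later negative is credited to SVR12, and the later positive does not enter Relapse12.

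**Illustration** (assumed: 90 ITT subjects, 86 with SVR12, exactly one such subject, no other exclusions)

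- Primary ITT: 86/90 = 95.6% under either label.
- mITT-GT-VF if the 10.1 definition governs: 86/90 = 95.6%.
- mITT-GT-VF if the reason category governs: 86/(90 − 1) = 86/89 = 96.6%.
- Second 10.5.1 approach: (86 + 1)/90 = 87/90 = 96.7%. It is 86/90 if the subject is not classed as missing.

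**Frequency** (no rate is in the documents)

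Assume 88 completers, a share m = 2–5% who miss the window but return later, and a relapse risk r = 2–4%. The chance of at least one such subject is 1 − (1 − m·r)^88.

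- Low end: 1 − (1 − 0.0004)^88 = 3%.
- High end: 1 − (1 − 0.002)^88 = 16%.

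This is an upper range, because r includes relapses already captured by Weeks 2–8. If only a quarter of relapses first appeared later (again assumed), the range would be 1 − (1 − 0.0001)^88 = 0.9% to 1 − (1 − 0.0005)^88 = 4.3%.

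**The case against.** The strongest reply is that the SAP already defines virologic failure, so mITT-GT-VF can be read from that definition. Where a narrower meaning is wanted, 10.7 says so by limiting virologic failure to post-treatment Week 12 and describing it as "non-responders due to on-treatment virologic failure or Relapse", with subscript 12. This is a fair reading, but it does not settle the matter. Section 10.8 lists missing SVR12 data as a non-virologic reason, and the 10.5.1 rule is tied to the reason category, not to the definition.

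A reader might go further and infer that the Week 12 relapse rate is biased downward, so that a later positive should count as Relapse12. The documents do not support that. Protocol 8.1.2.2 limits the endpoint to 12 weeks after the last dose, and the SAP itself provides for relapse after SVR12. A positive at Week 24 therefore does not show viraemia at Week 12, and counting it as Relapse12 could push the rate too high. Such a rule could also admit an unconfirmed value followed by a negative one.

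A reader might also infer that the relapse goes unreported. It does not: 10.7 requires a summary of completers meeting Relapse-overall, by SVR window and with subject number, and this subject appears there.

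Finally, the sentence that treats a quantifiable last value as a relapse might seem to resolve the case. Its own explanation limits it to waiving confirmation, so it does not extend the Relapse12 time limit.

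**Conclusion.** The definitions and the reason lists conflict for this narrow case, and nothing in either document reconciles them. The consequences are confined to the two reason tables, mITT-GT-VF and the analyses run on it, the PVF/non-PVF split, and the second 10.5.1 approach. For one such subject, the mITT-GT-VF rate differs by about 1 percentage point between readings, and 10.5.1 gains one success that observed data contradict. Both figures rest on the assumed 86/90 and a single case.

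The case is probably rare. The primary ITT result is unchanged, because the subject is an SVR12 failure under either label. The primary analysis follows post-treatment Week 12, so for some subjects the Week 24 value, and with it the conflict, may arise only in the final analysis. This is a minor clarification, worth making because it removes an observed failure from the success column of a sensitivity analysis.

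**What to change.** Make these changes to the SAP.

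1. In 5.1.2 and 10.8, state that mITT-GT-VF (subject to its genotype exclusion) and PVF keep every subject who meets the 10.1 virologic failure definition, and that such a subject is not in non-PVF.
2. In both reason lists in 10.1, add a reason ahead of the missing and other categories: relapse after a missing SVR12 window, meaning a subject who meets Relapse-overall. The 10.5.1 rule then no longer turns these subjects into successes.
3. Leave Relapse12 as the protocol defines it. Beside its rate, footnote the number of subjects in the new category, and say that a later negative is credited to SVR12 while a later positive does not enter Relapse12.

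The cost is a few lines of SAP text and one extra category to program. No new data are needed. The downside for the sponsor is slightly less favourable sensitivity figures if such a subject occurs.
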